2.3.3 Secondary and supportive endpoints

2.3.3.1 Secondary endpoints

Descriptive statistics of secondary endpoints

Mean and standard deviation of secondary endpoints at each visit, and changes of mean and standard deviation from baseline to each visit will be presented.

Analysis for Secondary endpoints of the same scale in M6,M9 and M12:

Using unimputed data of secondary endpoints with the same exploratory mixed-effects models as primary endpoints (i.e. the same scale in different time points will be included simultaneously), preferably generalized linear mixed model (GLMM) for repeated measures analysis. The statistical method is the same as primary analysis, per-protocol analysis and covariate-adjusted analysis for primary endpoints.

2.3.3.2 Supportive endpoints

Analysis for Effect endpoints:

- Change in hemoglobin concentration in cortical metabolism between M0 and M3:
Using Functional near-infrared spectroscopy (fNIRS) analysis, by Wuhan Yiruide Medical Treatment Equipment New Technology Co.,Ltd., with detailed procedure described in a separate file provided by the company.
- Change in intestinal flora between M0 and M3:
Using fecal metagenomics analysis², by Yunsheng Biotechnology Co(Shanghai, a company engaged in technology development and technical services in the field of biotechnology.), with detailed procedure described in a separate file provided by the company.
- Change in Serum metabolites level between M0 and M3:
Using non-targeted metabolomics analysis, by Yunsheng Biotechnology Co(Shanghai, a company engaged in technology development and technical services in the field of biotechnology.), with detailed procedure described in a separate file provided by the company.

Analysis for Safety endpoints:

Number of TEAEs, SAEs and AEs will be calculated as counts with proportion (%) in each group and in total from baseline at M0 to M3.

2.3.4 Other Sensitivity analysis

Complete data analysis

- **Handling of missing data for primary and secondary endpoints**

Missing at random (MAR) missingness mechanism is assumed for incomplete endpoints. For

missing data <50% of the endpoint, multiple imputation (MI) using regression (arbitrary missing pattern with 10 imputations) on missing data, dependent on baseline characteristics (age, sex), baseline scores is likely to be performed. Imputation will not be considered if missing data $\geq 50\%$ of the endpoint.

Therapy-adjusted analysis for primary endpoints

Based on covariate-adjusted analysis for primary endpoints, further adjusted for behavioral rehabilitation therapy (total class hours between M1,M2 and M3) to see the extent the effect size could be explained by the randomized intervention.

Analysis for sub-scales within the same primary endpoint

The statistical method is the same as descriptive statistics and primary analysis for primary endpoints. The analysis investigates if there are group-specific differences over time.

Analysis for sub-scales of certain ASD-related scale scores include:

- Gesell
 - Gesell DA adaptability
 - Gesell DA Fine movements
 - Gesell DA language
 - Gesell DA personal social
 - Gesell DA big movements
 - Gesell DQ adaptability
 - Gesell DQ Fine movements
 - Gesell DQ personal social
 - Gesell DQ big movements
- ATEC
 - Language
 - Social activity
 - Perception
 - Behavior
- SRS
 - Social perception
 - Social cognition
 - Social communication
 - Social motivation
 - SD behavior
- ASRS
 - Social/Communication
 - Unusual Behaviors

Dose-response analysis for primary endpoints

Using on-treatment period(see 2.2) for each subject, to perform dose-response analysis to see the effect of different on-treatment period (days without missed doses) on primary endpoints. The statistical method is the same as primary analysis. The analysis investigates if there are group-

specific differences over time.

Subgroup analysis

Subgroup analysis is not planned in this trial due to limited sample size.

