2.3.2 Primary endpoints

The primary endpoints are defined as change in scores of ASD-related scales from baseline at M0 to M3.

Descriptive statistics of primary endpoints

Mean and standard deviation of primary endpoints at each visit, and changes of mean and standard deviation from baseline to each visit will be presented.

Primary analysis for primary endpoints

Using unimputed data of primary endpoints in FAS, exploratory mixed-effects models, preferably generalized linear mixed model (GLMM) for repeated measures analysis, in the condition for endpoints of >2 visits. This analysis investigates if there are group-specific differences over time. The maximum likelihood method will be used to estimate the mean difference between the two groups and their 95% CI, with Gaussian distribution and identity link function; baseline score, group (group), time point (visit) and group \times visit interaction as fixed effects. The time point(visit) is treated as categorical variable in the models. Random slope with unstructured covariance will be preferred as priority; if convergence is not able to be achieved, random intercept will be performed as an alternative.

Otherwise, ANCOVA will be performed to estimate the mean difference between the two groups and their 95% CI, with group (group) as independent variable, and baseline score, time point (visit) and group \times visit interaction as covariates for outcomes with only 2 visits available. The available visits are defined as >10 observations at a single visit. The reason for this alternative method is explained in the Change Log.

For imputed data of primary endpoints, multiple imputation will be considered for handling missing outcomes. More details are described in 2.3.4.

Secondary analysis for primary endpoints

● Per-protocol analysis

Using unimputed data of primary endpoints in PPAS, exploratory mixed-effects models, preferably generalized linear mixed model (GLMM) for repeated measures analysis, in the condition for endpoints of >2 visits. Otherwise, ANCOVA will be performed if only 2 visits are available for the scores of ASD-related scales. The statistical method is the same as primary analysis for primary endpoints.

● Covariate-adjusted analysis

Covariate-adjusted analysis for primary endpoints is performed in FAS and PPAS using the same statistical method as primary analysis.

Covariates are baseline values (missing imputed) including:

- Age (years)
- Sex (1,Boy;2,Girl)

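### The only missing-outcome sensitivity analysis stays under MAR, leaves treatment group out of its listed imputation model, and uses 10 imputations

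*SAP*

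**What the plan says.** Section 2.3.2 sets the primary analysis: "Using unimputed data of primary endpoints in FAS, exploratory mixed-effects models", fitted by maximum likelihood with baseline score, group, visit and their interaction as fixed effects. ANCOVA replaces it where a scale has only two visits. The same section adds that "multiple imputation will be considered for handling missing outcomes" and refers to section 2.3.4.

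Section 2.3.4 states the assumption, "Missing at random (MAR) missingness mechanism is assumed for incomplete endpoints", and the method: "multiple imputation (MI) using regression (arbitrary missing pattern with 10 imputations) on missing data". The method applies to "missing data <50% of the endpoint". Its predictors and its status are given together: "dependent on baseline characteristics (age, sex), baseline scores is likely to be performed". From 50% upward no imputation is done, and no other analysis takes its place.

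No delta-adjusted, tipping-point or reference-based analysis appears in the SAP, and no random seed is given. The per-protocol, covariate-adjusted, therapy-adjusted, sub-scale and dose-response analyses leave the missingness assumption unchanged. The single imputation described in section 2.3.2 is for baseline covariates only.

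**The concern.** A sensitivity analysis for missing outcomes should relax the assumption behind the primary result. Here both analyses assume MAR. If families leave because the child is not improving, in a way that the observed data do not explain, nothing planned would reveal it.

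Two features make the imputation a poor check even under MAR. The listed predictors do not include randomized group, so missing outcomes in both arms would be drawn from one common regression, which dilutes any real difference. And 10 imputations are allowed up to just under 50% missing, with no fixed seed, while section 2.3 claims significance whenever the 95% CI excludes the null. A result near that limit could depend on the random draw.

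**Working it through.** The SAP gives no figure of its own to reproduce: section 2.1 states that no sample size calculation was made, and the 10 imputations and the 50% limit are design choices.

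**Inputs from the SAP.** 30 children per group (2.1); 10 imputations, applied below 50% missing, with age, sex and baseline scores as predictors (2.3.4); two-sided 95% CI rule (2.3).

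**Assumptions.** The fraction of missing information, f, is taken as up to about the missing share. The simulation values below are illustrative and not from the SAP.

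**1. Same assumption, and the effect of leaving group out.** A two-visit outcome was simulated with 30 per arm: 0.6 × baseline + 0.2 × age + 0.70 × group + residual of SD 0.8, with outcomes missing completely at random. Regression imputation used m = 10, with 400 repeats per row. Each cell shows the MI estimate, then the available-data estimate from the same runs.

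| Missing | Group in imputation model | Group omitted, as listed |
|---|---|---|
| 20% | 0.708 / 0.707 | 0.557 / 0.697 |
| 30% | 0.671 / 0.671 | 0.488 / 0.706 |
| 48% | 0.706 / 0.710 | 0.342 / 0.698 |

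With group included, MI returns the available-data answer, so agreement is no evidence about departures from MAR. With group omitted, the estimate shrinks roughly by the missing share: (1 − 0.20) × 0.70 = 0.56 and (1 − 0.48) × 0.70 = 0.36, against 0.557 and 0.342 simulated.

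**2. Monte Carlo error.** In units of the standard error this is about √(f/m).

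- f = 0.2, m = 10: √0.02 = 0.14
- f = 0.5, m = 10: √0.05 = 0.22
- f = 0.5, m = 50: √0.01 = 0.10

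Simulation with group included gave 0.139 at 20% missing and 0.218 at 48% with m = 10. For a result whose p would be 0.05 with unlimited imputations, the 95% range by seed is 2 × (1 − Φ(1.96 ± 1.96√(f/m))):

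- f = 0.2, m = 10: 0.025 to 0.092
- f = 0.5, m = 10: 0.016 to 0.128
- f = 0.5, m = 50: 0.031 to 0.078

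Relative efficiency, 1/(1 + f/m), is still 98% and 95% at m = 10. The loss is in reproducibility, hardly in precision.

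**3. Size of an undetected departure from MAR (scenario only).** The shift in the group difference is the missing share of the taurine arm times delta. With delta = 0.5 SD:

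- 20% missing: 0.20 × 0.5 = 0.10 SD
- 40% missing: 0.40 × 0.5 = 0.20 SD

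With 24 or 18 taurine children observed against 30 on placebo, the CI half-width is 1.96 × √(1/24 + 1/30) = 0.54 SD or 1.96 × √(1/18 + 1/30) = 0.58 SD. The shift is then about one fifth to one third of the half-width, which matters for a borderline result.

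**The case against.** The strongest reply is that the trial is exploratory, the main estimate comes from unimputed data, and the imputation does not drive it. That stands, and it limits the consequence.

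A reader might infer that the imputation tests nothing, or that both analyses must be biased in the same way. The SAP does not support this. The imputation adds age and sex, which the primary model lacks, so it conditions on a slightly different set. By omitting group it can also visibly disagree with the primary result. That disagreement would reflect dilution, however, and would say nothing about MAR.

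A reader might also take the change log as evidence of heavy dropout at M3. It records excess dropout at M6, M9 and M12 for Gesell, CARS and WISC only. If its count of fewer than 10 refers to children observed out of 60, an assumption suggested by the minimum-observation rule in section 2.3.2, more than 50/60 = 83% are missing there. Section 2.3.4 then excludes imputation altogether.

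Nor does 10 imputations make every result unstable. Seed noise matters when missing information is high and the result lies near the limit; a clear result with little missing data would not change.

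Finally, "arbitrary missing pattern with 10 imputations" may mean that visits are to be imputed jointly, which would bring in the other visits' scores. The listed predictors do not say so, and group would still be absent.

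**Conclusion.** The point holds in a limited form. Nothing planned examines departure from MAR, because the sole missing-outcome sensitivity analysis shares the assumption of the primary model. Read as listed, its imputation model pulls the group difference toward zero roughly in proportion to the missing share. Ten imputations leave Monte Carlo error of about 0.14 SE at 20% and 0.22 SE near 50% missing information, enough to decide a borderline claim.

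This rests on the predictor list being complete, on missing information being close to the missing share, and on illustrative simulation values. Missingness at M3 is unknown from the SAP, so the practical size cannot be fixed. Given the exploratory design, this should be corrected, but it does not undermine the primary estimate itself.

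**What to change.** Rewrite the missing-data paragraph of section 2.3.4 as follows.

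- Add treatment group and the scale's other available visits to the imputation model, or impute separately by arm.
- Use at least 50 imputations with a fixed seed.
- State that imputation will be performed when missing data are below 50%, in place of the present conditional wording there and in section 2.3.2.
- At M3, report a delta-adjusted analysis: shift imputed taurine-arm scores in the unfavourable direction for the scale, in fixed steps (for example 0 to 1 SD), up to the step at which the conclusion changes. Delta 0 is the MAR result.

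The first item must come before the last. Without group in the imputation model the delta-0 row is already shrunk, and the tipping point would mix dilution with the departure from MAR.

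The cost is SAP wording, minutes of computing and one extra table per scale. Section 1.1.3 lists ten primary scales, so that is up to ten tables.

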1.1.3 Endpoints

1.1.1.3 Primary endpoints

The primary endpoints addressing the primary objectives:

Change from baseline at month 0(M0) to month 3(M3) in:

- The Gesell score
- The Wechsler intelligence scale (WISC) score
- The Childhood Autism Rating Scale (CARS) score

Change from baseline at M0 to month 1(M1), month 2(M2), month 3(M3) in:

- The Autism Treatment Evaluation Checklist (ATEC) score
- The Autism Spectrum Rating Scales (ASRS) score
- The Social Responsiveness Scale (SRS) score
- The Identification and Management of Feeding Difficulties (IMFeD) score
- The Six Gastrointestinal Severity Index(6-GSI) score
- The Children's Sleep Habits Questionnaire (CSHQ) score
- The Parenting Stress Index (PSI)

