2.3.6 Statistical software

STATA® (version 15.1, Stata Corp, Texas, USA) will perform all data analyses and generate most data displays. R4.1.2 (Vienna, Austria) may also be used for some data analyses and generating statistical graphs.

3. Change log

Version	Date	Reasons for change
0.0	18 Aug 2023	Clinical Trial registration
1.0	7 Mar 2024	Clinical assessments at M1 and M2 were cancelled because clinicians found it difficult for subjects to keep intense clinical visits;
2.0	10 Jan 2025	Secondary endpoints updated
2.5	17 Feb 2025	Supportive endpoint analysis and Other sensitivity analysis updated.
3.0	28 Feb 2025	As drop-outs in M6,M9,M12 for Gesell, CARS and WISC are more than expected (<10 at each visit), ANCOVA will be preferred as an alternative.

4. Appendix

Table 1 The formulas for calculating Cohen's D values

Condition	Statistical display	Formula
-----------	---------------------	---------

Population estimated mean group difference in change over time	$\beta_{T-T0} (95\%CI)$	$\frac{\beta_{T-T0}}{(upperlimit - lowerlimit) \times \frac{2 \times 1.96}{\sqrt{N_{T-T0}}}}$
--	-------------------------	---

Abbreviations: A:placebo group; B, taurine group; T, time visit; T0,baseline.

Table 2 The formulas for calculating ASRS T-score

Condition	Age range	Raw score of items	Formula ¹
SC	2-5 years	$\Sigma (i1 i3 i4 i5 i7 i13 i14 i15 i16 i17 i18 i19 i21 i22 i24 i25 i28 i29 i30 i32 i33 i35 i36 i37 i38 i40 i43 i44 i49 i50 i51 i52 i54 i55 i57 i61 i62 i63 i67)$	$50+10 \times ((\text{raw score} - 50.06)/10.12)$
	6-18 years	$\Sigma (i3 i4 i8 i9 i12 i23 i28 i31 i32 i33 i39 i42 i43 i45 i55 i56 i61 i69 i7)$	$50+10 \times ((\text{raw score} - 24.3)/11.95)$
UB	2-5 years	$\Sigma (i2 i8 i9 i10 i11 i12 i20 i26 i27 i39 i41 i42 i45 i46 i47 i48 i53 i56 i60 i64 i65 i69 i70)$	$50+10 \times ((\text{raw score} - 50)/10.51)$
	6-18 years	$\Sigma (i2 i13 i17 i20 i21 i22 i24 i25 i26 i27 i29 i38 i40 i46 i48 i49 i50 i51 i54 i62 i63 i65 i67 i68)$	$50+10 \times ((\text{raw score} - 27.74)/10.79)$
Total	2-5 years	-	$50+10 * ((T \text{ score}_{SC+UB} - 50.03)/10.35)$
	6-18 years	-	$50+10 * ((T \text{ score}_{SC+UB} - 47.89)/7.85)$

¹the reference values for calculation are based on Chinese reference population^{3,4}.

Abbreviations: SC, Social/Communication; UB, Unusual Behaviors

5. References

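### The multiple-imputation model for missing outcomes omits randomised group, so its treatment estimate shrinks toward zero whenever there is a true effect

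*SAP*

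**What the plan says.** Section 2.3.2 bases the primary analysis on unimputed data in the full analysis set and refers to Section 2.3.4 for imputation of missing outcomes. Section 2.3.4 states: "Missing at random (MAR) missingness mechanism is assumed for incomplete endpoints". For endpoints with less than half their values missing it plans "multiple imputation (MI) using regression (arbitrary missing pattern with 10 imputations) on missing data". The predictors it names follow at once: "dependent on baseline characteristics (age, sex), baseline scores is likely to be performed". At or above 50% missing, no imputation is done.

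The mixed model in Section 2.3.2 has as fixed effects "baseline score, group (group), time point (visit) and group" × visit interaction. The ANCOVA used for two-visit outcomes also has group as the term of interest.

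Three further places decide how much help other visits could give:

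- Section 1.1.1.3 lists Gesell, WISC and CARS under "Change from baseline at month 0(M0) to month 3(M3) in", with no earlier on-treatment visit.
- Section 3 (Change log), version 3.0, begins "As drop-outs in M6,M9,M12 for Gesell, CARS and WISC are more than expected (<10 at each visit" and turns to ANCOVA for that reason.
- Section 2.3.2 says: "The available visits are defined as >10 observations at a single visit".

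**The concern.** An imputation model should contain every term of the analysis model that is to be estimated. Here the predictors are age, sex and baseline scores, and the wording does not leave the list open. Scores filled in this way have the same expectation in both arms given those predictors, so they dilute whatever group difference the observed scores show.

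This imputation is the SAP's planned check on missing outcomes, for primary and secondary endpoints. If it gives a smaller effect than the unimputed analysis, a reader cannot tell real sensitivity to missing data from shrinkage built in by the imputation model. A real effect could then be reported as fragile.

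**Working it through.** **Inputs from the SAP.** 60 subjects, 30 per group (Section 2.1); two-sided 95% intervals (Section 2.3); regression imputation with 10 imputations, allowed at any missing fraction below 50% (Section 2.3.4). The SAP states no power, effect-size or bias figure that could be reproduced.

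**Assumptions not in the SAP.** True difference 0, 0.50 or 0.70 SD; correlation 0.6 between baseline and follow-up; data missing completely at random (a special case of the SAP's assumption) and equally by arm; missing fraction *f* of 10, 20, 40 or 48%.

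**Step 1: expected value.** Let Δ be the true baseline-adjusted difference. The observed share (1 − *f*) contributes Δ to the contrast and the imputed share *f* contributes 0:

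E[estimate] ≈ (1 − *f*) × Δ + *f* × 0 = (1 − *f*)Δ.

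For Δ = 0.70: 0.90 × 0.70 = 0.63; 0.80 × 0.70 = 0.56; 0.60 × 0.70 = 0.42; 0.52 × 0.70 = 0.364.

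**Step 2: simulation with the listed predictors only.** Bayesian normal-regression imputation, 10 imputations, ANCOVA on group and baseline, Rubin's rules with small-sample degrees of freedom, 1,500 trials per cell.

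| Missing | 10% | 20% | 40% | 48% |
|---|---|---|---|---|
| True 0.70, group omitted | 0.633 | 0.554 | 0.406 | 0.355 |
| True 0.70, group included | 0.701 | 0.712 | 0.704 | 0.709 |
| True 0.70, unimputed ANCOVA | 0.706 | 0.702 | 0.698 | 0.703 |
| True 0.50, group omitted | 0.443 | 0.394 | 0.294 | 0.253 |
| Power at 0.70, omitted / included | 81 / 86% | 63 / 83% | 18 / 64% | 7 / 54% |
| Power at 0.50, omitted / included | 47 / 58% | 31 / 50% | 7 / 37% | 3 / 32% |
| Coverage at 0.70, omitted | 96.1% | 95.4% | 91.0% | 87.5% |
| Rejection with no effect, omitted | 2.5% | 1.2% | 0.3% | 0.0% |

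The means follow (1 − *f*)Δ. A separate simulation at 0.50 SD gave 0.450, 0.403, 0.299 and 0.248 at 10, 20, 40 and 49% missing, and 0.494 to 0.501 at those fractions with group included. At 49% missing, the mean standard error from Rubin's rules was 0.284 against an actual standard deviation of 0.164. The intervals are therefore too wide as well as centred too low, which is why power falls so far while coverage mostly holds. For true effects of 0 to 0.50 SD, coverage was 95 to 100%.

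**Step 3: other visits of the same scale imputed jointly.** A routine for arbitrary missing patterns may use these, and they carry part of the group contrast. With one other visit fully observed and Δ = 0.70:

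| Between-visit correlation | 10% | 20% | 40% | 48% |
|---|---|---|---|---|
| 0.7 | 0.667 | 0.636 | 0.581 | 0.569 |
| 0.8 | 0.679 | 0.661 | 0.619 | 0.615 |
| 0.9 | 0.691 | 0.671 | 0.665 | 0.662 |

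At correlation 0.8 the shrinkage is 1 − 0.679/0.70 = 3%, then 6%, 12% and 12%. Across the table it runs from 1% (1 − 0.691/0.70) to 19% (1 − 0.569/0.70).

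**Step 4: Gesell, CARS and WISC.** I read the change log's figure as fewer than 10 observations at each of M6, M9 and M12. That reading fits the switch to ANCOVA and the SAP's rule for an available visit. With another visit seen in 9 of 60 subjects (correlation 0.8, 500 trials per cell), Δ = 0.70 becomes 0.655/0.567/0.426/0.369, a loss of 6/19/39/47%. Such a visit is 51/60 = 85% missing, so the SAP's own ceiling would bar imputing it. The M3 imputation then reduces to Step 2, with almost the same loss.

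**The case against.** Several points on the other side stand:

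- The imputation is one sensitivity analysis in an exploratory trial, and its wording is tentative. The primary, per-protocol and secondary analyses use unimputed data and are untouched.
- The bias exists only if the true effect is not zero, and rejection under no effect stays below the nominal 5%.
- The SAP gives no missing fraction at M3. The most striking losses sit near the 50% ceiling; at 10% missing, power is 81% against 86%.
- On the reading of the change log used here, Gesell, CARS and WISC at M6, M9 and M12 are too incomplete to be imputed, so those secondary endpoints are not exposed.
- The rule for an available visit governs the choice between mixed model and ANCOVA, not what may enter an imputation model. It supports the reading of the change log and nothing more.
- Under the same missing-at-random assumption, the corrected imputation nearly reproduces the unimputed ANCOVA, so it is a modest check even when done properly.

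None of this supplies the missing term. The tentative wording concerns whether imputation is run, not how. Bringing in other visits reduces the shrinkage without removing it. An analyst might add group unprompted, but a choice that can move the estimate by almost half should be written down.

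**Conclusion.** The concern holds. As specified, the imputation omits the effect being estimated, and no other section repairs this. With the listed predictors only, the treatment estimate loses about the missing fraction of any true effect, up to nearly half at the SAP's ceiling. If another well-observed visit is imputed jointly, the loss is about 1 to 19%. These sizes rest on the assumed effect, the correlations and equal, completely random missingness. The direction needs only a non-zero effect and some missing outcomes. The error is conservative: it cannot by itself produce a false claim of benefit, and intervals mostly keep their coverage, dropping below 95% only at 0.70 SD with 40% or more missing. What it damages is the interpretation of the missing-data check, so it should be corrected before that analysis is run.

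**What to change.** In Section 2.3.4, include randomised group in every imputation equation, or impute separately by arm. State also that scores on the same scale at other available visits enter the imputation where they exist. For Gesell, CARS and WISC few exist, so there the group term is what removes the bias. The cost is one added term in the imputation command and one sentence in the SAP, with no new data.

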1.1.2 Objective(s)

1.1.1.1 Primary objective

To compare the effect of 3-month taurine supplementation (age-specific doses, 3 times/day) plus behavioral rehabilitation therapy versus placebo plus behavioral rehabilitation therapy on better rehabilitation of ASD core syndrome, reflected by differential age-specific ASD questionnaires evaluation from baseline at month 0 to month 3.

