1.1.4 Type of trial

This is a 3-month intervention with a total of 12-month follow-up, randomized, double-blind, placebo-controlled, two-armed, parallel group, single-center, exploratory trial comparing taurine supplementation (age-specific doses, 3 times/day) with placebo on better rehabilitation of ASD core syndrome in ASD children aged 2-18 years.

2. Statistical considerations

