2.1 Sample size determination

Sample size calculation is precluded from this trial due to exploratory design, as well as a lack of literature and data. 60 subjects (30 per group) are expected to meet the regular outpatient workload in the study site, which will be expected to reach the size within a year.

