2.2 Definition of analysis sets

- The full analysis set (FAS):
includes all randomized subjects according to the intention-to-treat (ITT) principle, regardless of actual treatment subjects receive. If any subject fails to complete at least one evaluation after randomization, modified ITT will be used as FAS instead.
- The per-protocol analysis set (PPAS):
includes all randomized subjects who receive and complete the randomized intervention during the whole intervention period (i.e. M0 to M3).
- The safety analysis set (SAS):

includes all randomized subjects exposed to at least one dose of randomized treatment. Any observation excluded from the analysis will be documented before database lock with the reason for exclusion provided.

Two observation periods are defined for each subject:

- In-trial: The in-trial period is defined as the uninterrupted time interval from date of randomization to date of last contact with trial site.
- On-treatment: The on-treatment period will therefore be from the date of first trial product administration to date of last trial product administration excluding potential off-treatment time intervals triggered by at least 7-day missed doses.

The in-trial and on-treatment periods define the patient years of observation and patient years of intervention, respectively, as the total time duration in the periods.

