2.3.1 Baseline characteristics

Baseline characteristics of subjects are defined as baseline values of the last available and eligible observation at or before randomization covering all subjects, including:

- Continuous:
 - Age (years)
 - Birth weight (kg)
 - Body Mass Index
 - Serum taurine concentration (relative concentration standardized by quality-control samples)
- Categorical:
 - Sex (1,Boy;2,Girl)
 - Nationality (1,Han; 2,Other)
 - Residential area (1,Urban;2, Rural)
 - Household monthly income (1,<=8500;2,>8500 and <20000;3,>=20000 and <50000; 4,>=50000)
 - Number of siblings (0,Single child; 1,One; 2,Two or more)

- Nourish style (0,Parental; 1,Grandparental; 2,Mixed)
- Paternal occupation (1,Civil servant;2 Farmer;3,Techican;4, Freelancer)
- Maternal occupation (1,Civil servant;2 Farmer;3,Techican;4, Freelancer)
- Allergy history (0,No; 1, Yes)
- Birth defects (0,No; 1, Yes)
- Abnormal birth history (0,No; 1, Yes)
- Serious medical history (0,No; 1, Yes)
- Receiving intervention previously (0,No; 1, Yes)
- Baseline physical examination (0,Normal; 1,Abnormal)
- ASD severity (0, Normal;1,Marginal;2,Mild;3,Medium;4,Severe;5,Extremely severe)

Baseline characteristics of subjects will be presented as mean and standard deviation for continuous variables with normal or approximately normal distribution; otherwise, median values and interquartile range (IQR) will instead be calculated. Categorical variables will be described as proportions(number of subjects within category \div all subjects $\times 100\%$).

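### The therapy-adjusted sensitivity analysis adds class hours accrued after randomisation, so it cannot show how much of the effect is due to the randomised treatment (minor)

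*SAP*

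**What the plan says.** Under SAP section 2.3.4, Therapy-adjusted analysis for primary endpoints, the covariate-adjusted model is "further adjusted for behavioral rehabilitation therapy (total class hours between M1,M2 and M3"). The stated aim is "to see the extent the effect size could be explained by the randomized intervention".

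Four other places in the SAP fix what this means:

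- **The model being extended** (2.3.2) holds only pre-treatment variables: "Covariates are baseline values (missing imputed) including" age, sex and serum taurine, plus others if they are imbalanced.
- **Baseline** (2.3.1) means "baseline values of the last available and eligible observation at or before randomization covering all subjects".
- **The treatment period** appears in the per-protocol definition (2.2), which requires subjects to "complete the randomized intervention during the whole intervention period (i.e. M0 to M3").
- **The primary objective** (1.1.1.1) compares "taurine supplementation (age-specific doses, 3 times/day) plus behavioral rehabilitation therapy versus placebo plus behavioral rehabilitation therapy". Behavioural therapy is therefore background treatment in both arms.

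The SAP does not say that class hours are fixed or that they are assumed to be unaffected by allocation. It plans no comparison of hours between arms, names no mediation estimand, and gives no caution about interpreting this model.

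**The concern.** Class hours are the only variable in this model that arises after randomisation. A child who improves may take more classes, or may need fewer. A family's engagement may drive both the hours and the scores. In either case hours can differ between arms as a consequence of treatment, and conditioning on them breaks the comparison that randomisation protects.

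What is at stake is a stated inference. If the coefficient shrinks when hours are added, the report could say that therapy rather than taurine explains the effect. If it grows, the report could credit taurine with more than allocation produced. Section 2.3 allows a significant difference to be claimed for effect endpoints whenever the 95% interval excludes the null, and nothing exempts this model.

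**Working it through.** The plan gives no figure to reproduce. The check has two parts.

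**1. Timing.** Baseline ends at randomisation (2.3.1). Treatment runs from M0 to M3 (2.2). Hours accumulated up to M3 therefore fall inside the treatment period and are not baseline under the SAP's own definition.

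**2. What the adjusted coefficient estimates.** Let T be arm, H class hours, U an unmeasured common cause with variance 1, and Y the outcome:

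- H = aT + cU + e, scaled so that Var(H given T) = 1
- Y = τT + bH + gU + e, with residual SD 1

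Substituting H into Y gives the total effect of allocation, **τ + ab**.

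Given T and H, the expected value of U is c(H − aT). So E[Y given T, H] = (τ − acg)T + (b + cg)H, and the hours-adjusted coefficient of T is **τ − acg**.

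Three cases follow:

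- a = 0: both equal τ, so nothing is distorted.
- a ≠ 0 and cg = 0: the adjusted value is τ, the direct effect, and the part ab acting through hours is dropped.
- a ≠ 0 and cg ≠ 0: the adjusted value is neither the total nor the direct effect.

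**Illustration.** Every input is an assumption, because the SAP supplies none: τ = 0.4, b = 0.2, and c = g = 0.5 where a common cause is present. The shift a is varied in both directions.

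| a | Total, τ + ab | Adjusted, no common cause | Adjusted, c = g = 0.5 |
|---|---|---|---|
| −0.5 | 0.30 | 0.40 | 0.525 |
| −0.2 | 0.36 | 0.40 | 0.45 |
| 0 | 0.40 | 0.40 | 0.40 |
| 0.2 | 0.44 | 0.40 | 0.35 |
| 0.5 | 0.50 | 0.40 | 0.275 |

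Example, last row: total 0.4 + 0.5 × 0.2 = 0.50; adjusted 0.4 − 0.5 × 0.5 × 0.5 = 0.275.

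As a share of the total effect:

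- Hours raised, no common cause: 0.40/0.44 = 91% to 0.40/0.50 = 80%.
- Hours raised, common cause: 0.35/0.44 = 80% to 0.275/0.50 = 55%.
- Hours lowered, common cause: 0.45/0.36 = 125% to 0.525/0.30 = 175%.

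**Check of the formulas.** In 4,000 simulated trials of 30 per arm with τ = 0.5, b = 0.3 and c = g = 0.5, the results were:

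- a = 0.2: simulated total 0.558 and adjusted 0.450 (formulas 0.56 and 0.45).
- a = 0.5: simulated total 0.648 and adjusted 0.373 (formulas 0.65 and 0.375).

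With τ = 0 and the other values unchanged, the formulas give totals of +0.06 and +0.15 against adjusted values of −0.05 and −0.125. The sign can therefore reverse.

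**The case against.** The strongest reply is that this is one sensitivity model in a "randomized, double-blind, placebo-controlled, two-armed, parallel group, single-center, exploratory trial", and that checking a result against a co-intervention is common. With a plan in which "60 subjects (30 per group) are expected to meet the regular outpatient workload in the study site", hours can differ between arms by chance. The primary and covariate-adjusted models leave hours out, so the total effect remains available beside this one. All of that stands, and it is why the point is minor.

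Second, the aim could be read as separating taurine's own effect from that of therapy. With no common cause, the adjusted coefficient is exactly the assumed direct effect of 0.40. This also stands: the 91% to 80% in that scenario is the direct share correctly recovered, not bias against that aim. An error against it needs a shared cause of hours and scores, which the SAP neither assumes away nor addresses.

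Third, the effect is small beside the noise. With a within-arm SD of 1, the standard error of a difference is √(2/30) ≈ 0.26 before baseline adjustment. The gaps between total and adjusted effects above are a(b + cg), from 0.2 × 0.2 = 0.04 to 0.5 × 0.45 = 0.225, all below one standard error. That is fair on practical weight. It does not rescue the stated reading, because both models are fitted to the same children and the plan proposes to interpret the change between them.

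Three stronger readings are tempting and not supported:

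- **That this analysis is biased in this trial.** Nothing in the SAP shows that hours respond to treatment. Blinding removes a response to known allocation, though not one to the child's condition. A schedule of hours may be set in the protocol, which is not shown. The SAP also speaks of total hours, not of hours attended.
- **That adjustment always shrinks the effect.** It inflates it if treatment lowers hours.
- **That hours from M0 to M1 are left out.** The phrase may equally mean hours recorded at the three visits, which would cover M0 to M3. The window is unclear, but not shown to be short.

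**Conclusion.** The concern holds as a point about interpretation. The hours-adjusted coefficient cannot bear the meaning the SAP gives it. If allocation leaves hours unchanged, adjustment at most changes precision and reveals nothing about what the treatment explains. If allocation changes hours, the coefficient drops the pathway through them, and with a shared cause of hours and scores it is not the direct effect either.

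Under the assumed inputs with a common cause, the adjusted value ranges from 55% to 175% of the total effect across shifts in hours of +0.5 to −0.5 SD, and equals it at zero shift. These figures show direction and mechanism only; they do not estimate what will happen in this trial.

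A reader might infer that the trial's treatment effect is compromised. It is not: the primary analysis in 2.3.2 does not use hours. Severity: minor.

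**What to change.** In SAP section 2.3.4:

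1. Remove the statement that this analysis shows how far the randomised intervention accounts for the effect, and state that the estimate without hours is the treatment effect.
2. Tabulate class hours by arm.
3. State whether the hours window covers all of M0 to M3.
4. Label the hours-adjusted model as an exploratory, non-causal association, because hours accrue after randomisation and may respond to treatment.

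A baseline substitute is not a ready alternative. The item on previous intervention is a yes/no history variable already on the conditional covariate list, and it does not measure concurrent therapy. Hours planned at M0 are not shown to be collected.

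The cost is a few sentences and one table from data this model already needs. If hours before M1 were not recorded, the table covers only the recorded window and should say so. The downside is that this model can no longer support a claim about how much of the effect is due to taurine.
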